#### **5.2. Vital Signs and Physical Examinations**

Descriptive statistics of vital sign parameters will be summarized at each scheduled time point per vaccination group. A full physical examination is only conducted at screening. At other visits, only abbreviated, symptom-directed examinations are performed per the investigator's discretion and the clinically significant abnormal findings are recorded as AEs and will be analyzed as such. Therefore, no separate analysis of physical examination findings will be performed.

### **6. IMMUNOGENICITY ANALYSIS**

#### **6.1. Parameters**

Humoral immune responses as measured by the following assays will be analyzed:

- Binding antibody concentrations using Filovirus Animal Nonclinical Group (FANG) ELISA (ie, quantification of antibodies binding to EBOV GP using the EU/mL readout).
- Neutralizing antibodies against the Ad26 vector using an Ad26 VNA readout (IC90 titers).

#### **6.2. Handling of Missing and/or Unquantifiable Immunogenicity Data**

For the generation of summary statistics, values of the EBOV GP binding antibody concentrations (EU/mL) and Ad26 VNA (IC90 titers) that are below the lower limit of quantification (LLOQ) will be imputed with half of the corresponding LLOQ (ie, LLOQ/2) and values above the upper limit of quantification (ULOQ) will be imputed with the corresponding ULOQ. For the calculation of fold changes, the values below LLOQ will be imputed with the corresponding LLOQ and values above the ULOQ will be imputed with the ULOQ.

#### **6.3. Immunogenicity Data Analysis**

##### **6.3.1. Immunogenicity Against the Insert**

The following will be defined for binding antibody concentrations as measured by EBOV GP FANG ELISA (EU/mL):

- **Sample interpretation:** A sample will be considered positive, if the value is above the LLOQ.
- **Responder:**
  - If sample interpretation is negative at baseline but positive post-baseline and the post-baseline value is greater than 2.5×LLOQ; OR
  - If sample interpretation is positive at both baseline and post-baseline and there is a greater than 2.5-fold increase from baseline (2.5-fold increase on the original scale).

##### ***Primary Analysis***

To assess the primary objective, only participants included in the per protocol analysis set will be considered. Estimated differences in the ELISA concentrations (EU/mL) at 21 days post Dose 2 will be

expressed as ratio of GMCs with corresponding 95% CI. This will be determined by comparing log10-transformed binding antibody concentrations (EU/mL) between the groups and back-transformation of the estimated difference and corresponding 95% CI. Equivalence of any 2 groups will be established if the 95% CI of the estimated GMC ratio lies entirely within the range of 0.5 to 2.0. Immunogenic equivalence of the 3 different lots of Ad26.ZEBOV (Lots A, B, and C) paired sequentially in 3 groups with 3 different lots of MVA-BN-Filo (Lots 1, 2, and 3) will be established if equivalence is shown for all 3 pairwise comparisons. An analysis of variance model will be used to estimate the GMCs (with the observed binding antibody concentrations [EU/mL] at 21 days post dose 2 as response and group [lot] as the independent variable).

### ***Other Analysis***

The secondary objective will be assessed similar to the primary objective, but at 56 days post Dose 1. Equivalence of the 3 different lots of Ad26.ZEBOV (Lots A, B, and C) will be established if equivalence is shown for all 3 pairwise comparisons (Lots A vs B, A vs C and B vs C) at 56 days post Dose 1.

As sensitivity analyses to the widened window around Dose 2 administration for the main part of the study (Groups 1-4) under CTP Amendment 3, both the primary and secondary hypotheses will also be tested as sensitivity analysis based only on data of participants who received the second vaccination within the original (ie,  $\pm 3$  days) window around the Day 57 visit.

The following outputs will also be generated and presented by vaccination groups:

- Table of summary statistics (including geometric means and corresponding 95% CIs, geometric mean fold increase [from Pre-dose 1, Pre-dose 2 and Pre-booster] with corresponding 95% CI), responder rates and positive sample interpretation (ie, showing number, percentage and the exact 95% Clopper-Pearson CI) at all available time points.
- Dot plots (on a log10-scale) with distinction between positive and negative sample interpretations at all available time points.
- Graphic (on a log10-scale) of regimen profiles (ie, geometric mean concentrations with 95% CIs over time).
- Reverse cumulative distribution curve using binding antibody concentrations (log10-scale) by percent of participants with antibody concentrations at baseline and each post-baseline visit time point.
- Data listing.

To evaluate the potential impact of delayed (ie, outside the widened window due to COVID-19 pandemic) Dose 2 vaccination on the immune response, the following additional outputs will be generated (only if more than 10% of participants in the immunogenicity subset receive delayed [ie, outside the -3/+28 days window around Day 57] Dose 2 vaccination) for the binding antibody concentrations and presented for participants having received Dose 2 vaccination within the -3/+28 days window around the Day 57 visit (as defined in CTP Amendment 3) window versus those having received Dose 2 outside that window:

- Table of summary statistics (including geometric means and corresponding 95% CIs, geometric mean fold increase [from Pre-dose 1 and Pre-dose 2] with corresponding 95% CI), responder rates and positive sample interpretation (ie, showing number, percentage and the exact 95% Clopper-Pearson CI) at all available time points.
- Dot plots (on a log10-scale) with distinction between positive and negative sample interpretations at all available time points.
- Scatter plot of the 21 days post Dose 2 immune response versus the elapsed time (days) between Doses 1 and 2 vaccinations.

### **6.3.2. Immunogenicity Against the Vector**

For the booster cohort, the following will be defined for Ad26 VNA titers (IC90 titers):

**Sample interpretation:** a sample will be considered positive, if the value is above the assay-specific LLOQ.

The following outputs will be generated and presented by vaccination groups (ie, only Groups 5 and 6):

- Table of summary statistics (including geometric means and corresponding 95% CIs) and positive sample interpretation (ie, showing number, percentage and the exact 95% Clopper-Pearson CI).
- Dot plots (on a  $\log_{10}$ -scale) with distinction between positive and negative sample interpretations.
- Scatter plot (on a  $\log_{10}$ -scale) of binding antibody responses (EU/mL) against Ad26 VNA (IC90 titers) at various time points (with Spearman's correlation coefficients).
- Data listing.

## ATTACHMENTS

### 1. TOXICITY TABLES FOR USE IN STUDIES ENROLLING HEALTHY ADULTS

The abbreviations used in the following tables are:

FEV1: forced expiratory volume in 1 second; IV: intravenous; Rx: therapy

#### CLINICAL ADVERSE EVENTS

Grading scale used for clinical adverse events is adapted from the Division of Microbiology and Infectious Diseases (DMID) Toxicity Tables (2007). For adverse events not included in the tables below, refer to the severity criteria guidelines in Section 12.1.3 of the CTP.

Cardiovascular	Grade 1	Grade 2	Grade 3
Arrhythmia		Asymptomatic, transient signs, no Rx required	Recurrent/persistent; symptomatic Rx required
Hemorrhage, blood loss	Estimated blood loss ≤100 mL	Estimated blood loss >100 mL, no transfusion required	Transfusion required
Respiratory	Grade 1	Grade 2	Grade 3
Cough	Transient; no treatment	Persistent cough	Interferes with daily activities
Bronchospasm, acute	Transient; no treatment; FEV 1 71%-80% of peak flow	Requires treatment; normalizes with bronchodilator; FEV 1 60%-70% (of peak flow)	No normalization with bronchodilator; FEV 1 <60% of peak flow
Dyspnea	Does not interfere with usual and social activities	Interferes with usual and social activities, no treatment	Prevents daily and usual social activity or requires treatment
Gastrointestinal	Grade 1	Grade 2	Grade 3
Nausea/vomiting	Minimal symptoms; caused minimal or no interference with work, school or self-care activities	Notable symptoms; required modification in activity or use of medications; did not result in loss of work or cancellation of social activities	Incapacitating symptoms; required bed rest and/or resulted in loss of work or cancellation of social activities
Diarrhea	2-3 loose or watery stools or <400 g/24 hours	4-5 loose or watery stools or 400-800 g/24 hours	6 or more loose or watery stools or >800 g/24 hours or requires IV hydration

Reactogenicity	Grade 1	Grade 2	Grade 3
Local reactions			
Pain/tenderness at injection site	Aware of symptoms but easily tolerated; does not interfere with activity; discomfort only to touch	Notable symptoms; required modification in activity or use of medications; discomfort with movement	Incapacitating symptoms; inability to do work or usual activities; significant discomfort at rest
Erythema/redness a	2.5-5 cm	5.1-10 cm	>10 cm
Induration/swelling b	2.5-5 cm and does not interfere with activity	5.1-10 cm or interferes with activity	>10 cm or prevents daily activity
Itching at the injection site	Minimal symptoms; caused minimal or no interference with work, school, or self-care activities	Notable symptoms; required modification in activity or use of medications; did not result in loss of work or cancellation of social activities	Incapacitating symptoms; required bed rest and/or resulted in loss of work or cancellation of social activities
Systemic reactions			
Allergic reaction	Pruritus without rash	Localized urticaria	Generalized urticaria; angioedema or anaphylaxis
Headache	Minimal symptoms; caused minimal or no interference with work, school or self-care activities	Notable symptoms; required modification in activity or use of medications; did not result in loss of work or cancellation of social activities	Incapacitating symptoms; required bed rest and/or resulted in loss of work or cancellation of social activities
Fatigue/malaise	Minimal symptoms; caused minimal or no interference with work, school or self-care activities	Notable symptoms; required modification in activity or use of medications; did not result in loss of work or cancellation of social activities	Incapacitating symptoms; required bed rest and/or resulted in loss of work or cancellation of social activities
Myalgia	Minimal symptoms; caused minimal or no interference with work, school or self-care activities	Notable symptoms; required modification in activity or use of medications; did not result in loss of work or cancellation of social activities	Incapacitating symptoms; required bed rest and/or resulted in loss of work or cancellation of social activities

a In addition to grading the measured local reaction at the greatest single diameter, the measurement should be recorded as a continuous variable.

b Induration/swelling should be evaluated and graded using the functional scale as well as the actual measurement.

Reactogenicity (continued)	Grade 1	Grade 2	Grade 3
Arthralgia	Minimal symptoms; caused minimal or no interference with work, school or self-care activities	Notable symptoms; required modification in activity or use of medications; did not result in loss of work or cancellation of social activities	Incapacitating symptoms; required bed rest and/or resulted in loss of work or cancellation of social activities
Chills	Minimal symptoms; caused minimal or no interference with work, school or self-care activities	Notable symptoms; required modification in activity or use of medications; did not result in loss of work or cancellation of social activities	Incapacitating symptoms; required bed rest and/or resulted in loss of work or cancellation of social activities

### VITAL SIGNS TOXICITY GRADING

Grading scale used for vital signs is according to DMID Toxicity Tables (2007)

Vital Signs	LO/HI/N a	Mild (Grade 1) b	Moderate (Grade 2)	Severe (Grade 3)
Fever (°C) c	HI	38.0-38.4	38.5-38.9	>38.9
Fever (°F)	HI	100.4-101.1	101.2-102.0	>102.0
Tachycardia	HI	101-115 bpm	116-130 bpm	>130 bpm or ventricular dysrhythmias
Bradycardia	LO	50-54 or 45-50 bpm if baseline <60 bpm	45-49 or 40-44 bpm if baseline <60 bpm	<45 or <40 bpm if baseline <60 bpm
Hypertension (systolic) - mm Hg d	HI	141-150	151-160	>160
Hypertension (diastolic) - mm Hg	HI	91-95	96-100	>100
Hypotension (systolic) - mm Hg	LO	85-89	80-84	<80
Tachypnea - breaths per minute	HI	23-25	26-30	>30

a Low, High, Not Graded.

b If initial bound of grade 1 has gap from reference range or eligibility range, calculations based on the New England Journal of Medicine (NEJM) reference ranges.

c Oral temperature.

d Assuming participant is awake, resting, and supine; for adverse events, 3 measurements on the same arm with concordant results.

## 2. PERIOD/PHASE ALLOCATION OF ADVERSE EVENTS

Solicited events are always allocated to the respective post-dose period. Adverse events will be allocated to analysis periods/phases by following the following steps:

### Step 1: Allocation of events to the periods:

Adverse events in the SDTM database are allocated to periods/phases based on their start date/time. If the start date/time of an event falls between (or on) the start and stop date/time of a period, the AE is attributed to that period (treatment-emergent principle).

- In case of partial start or stop dates (ie, time and/or day and/or month and/or year missing), the events are allocated to the periods using the available partial information on start and end date; no imputation will be done. If, for instance, the AE start date only month and year are available, these data are compared to the month and year information of the periods. This rule may lead to multiplication of the event as a consequence of its assignment to multiple periods.
- In case of a completely missing end date, the date is imputed by the cut-off date of the analysis for participants still ongoing in the study, and by the end date of the last period for participants who discontinued or completed the trial. In case of a completely missing start date, the event is allocated to the first active treatment phase (post dose 1 period), except if the end date of the AE falls before the start of the first active treatment phase (post-dose 1 period).

### Step 2: Combination of events:

Overlapping/consecutive events are defined as events of the same subject with the same preferred term which have at least 1 day overlap or for which the start date of an event is 1 day after the end date of the preceding event. Overlapping/consecutive events may be combined into one AE or not, according to the following rules:

- 1) If overlapping/consecutive events start in one of the following periods - Screening or post dose extension (ie, non-active periods) - followed by an AE in - post-dose period (active period) - they are allocated to their respective periods and are considered as separate events.
- 2) In case overlapping/consecutive events start within a single period, they are considered as one and the same AE. The individual events which contribute to this AE are retained as individual records in the ADaM database but are assigned the same onset, period, and total duration. All related attributes to the AE/phase/period should also be consistent with the new event.
- 3) In case overlapping/consecutive events start in both an active period followed by a non-active period, they are allocated to the active period only and are considered as one and the same AE. The individual events which contribute to this AE are retained as individual records in the ADaM database but are assigned the same onset, treatment period, and total duration. All related attributes to the AE/phase/period should also be consistent with the new event.
- 4) In case an active period is followed by another active period, and the overlapping/consecutive events start in both periods, they are allocated to their respective period and are considered as separate AEs. The same rule applies for 2 non-active periods.

## Remarks:

1. Events can only be combined into one and the same AE if their start and stop dates are known.
2. In case the completely missing end date is imputed (for period allocation), this date is also considered as a complete date.
3. Time is not considered when determining overlap of events.

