### 5.1.2. Analysis of Adverse Events

Number and percentage of participants with at least one particular AE (unsolicited/solicited) will be tabulated. Unsolicited AEs will be summarized by System Organ Class and Preferred Term. Solicited AEs will be summarized by class (local, systemic) and preferred term.

The following tables will be generated for solicited AEs: summary (ie, any solicited AE, solicited AE with Grade 3 severity, any solicited local AE, solicited local AE with Grade 3 severity, any solicited systemic AE, solicited systemic AE with Grade 3 severity, and solicited systemic AE considered related to vaccine), by worst severity grade, Grade 3, related (systemic only), time to onset (in days) and duration (in days) for most frequent events and body temperature. Note that duration is defined as number of days from the start of the event until resolution of the event. The time to first onset is defined as (date of first onset – reference date + 1). The reference date is the start date of the vaccination period.

For unsolicited AEs, the following tables will be generated: summary table (including any unsolicited AE, unsolicited AE with severity Grade 1 as worst grade, unsolicited AE with severity Grade 2 as worst grade, unsolicited AE with severity Grade 3 as worst grade, unsolicited AE considered related to vaccine, unsolicited AE leading to permanent stop of study vaccine, SAE, SAE considered related to vaccine, COVID-19 related AE, AEs with fatal outcome), all events, most frequent, Grade 3, AEs leading to permanent stop of vaccination, related and SAE.

Listings and/or participant narratives will be provided as appropriate, for those participants who die, discontinue study vaccination due to an AE, experience a Grade 3 AE considered related to vaccination, experience an SAE, experience a SARS-CoV-2 infection (COVID-19) or vaccine misallocation.

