#### **5.1.4. Missing Data**

Missing data will not be imputed. Participants who do not report an event will be considered as participants without an event. An AE with a missing severity or relationship will be considered as an AE reported, but will be considered as not reported for the severity or relationship. For example, an AE with missing severity will be considered as an AE reported for the analysis of any grade, but will be considered as not reported for the analysis of Grade 3.

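### SAP Attachment 2, Remark 2 lets an imputed AE end date count as known even when the event is not recorded as ongoing, so a later SAE in follow-up can be merged into the preceding 28-day post-dose period

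*SAP*

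**What the plan says.** The rules are all in SAP Attachment 2.

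- **Step 1, imputation.** When an AE end date is completely missing, "the date is imputed by the cut-off date of the analysis for participants still ongoing in the study". Where follow-up has finished, the missing date is filled instead "by the end date of the last period for participants who discontinued or completed the trial". Partial dates are used as they stand and are not imputed.
- **Step 2, overlap.** Overlapping records are "events of the same subject with the same preferred term which have at least 1 day overlap". Records on consecutive days are treated in the same way.
- **Step 2, rule 2.** Overlapping records that start within one period become one AE with a common onset, period and total duration.
- **Step 2, rule 3.** When the first record starts in an active (post-dose) period and the next in a non-active period, "they are allocated to the active period only and are considered as one and the same AE", again with a common onset and total duration.
- **Step 2, rules 1 and 4.** Overlaps from non-active to active, from active to another active period, or between two non-active periods stay separate.
- **Remark 1.** "Events can only be combined into one and the same AE if their start and stop dates are known".
- **Remark 2.** "In case the completely missing end date is imputed (for period allocation), this date is also considered as a complete date".

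Elsewhere, SAP 5.1.2 states for solicited events that "duration is defined as number of days from the start of the event until resolution of the event". SAP 5.1.4 says of adverse event data generally: "Missing data will not be imputed". SAP 5 presents safety by post-dose period, and SAP 5.1.1 tabulates SAEs over the whole study.

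**The concern.** Remark 1 is a safeguard: records are not joined unless it is known when they began and ended. Remark 2 lifts it for records whose end is entirely unknown. That is sensible for an event still present at the cut-off. It is not sensible for an event that ended on an unrecorded date, and Attachment 2 does not distinguish the two.

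The exposed records are mostly SAEs. Under Protocol 12.3.1 most nonserious events are collected only to 28 days after each dose, while SAEs are collected to the end of the study. A same-term record that rule 3 can pull back out of follow-up is therefore usually an SAE. At stake are its period and onset date, and so the period-specific SAE rate. A secondary issue is that a combined duration can run to an administrative date instead of to resolution.

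**Working it through.** The plan gives no figure to reproduce, so the check applies its rules to example records.

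**Inputs from the documents.** SAP Table 3 ends each active period 28 days after the dose. With Dose 2 on Day 57, post-dose 2 runs from Day 57 to 57 + 28 = Day 85. Post-dose 2 follow-up then runs from Day 86 to the last contact, nominally Day 237 (Protocol 3.1).

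**Assumed.** The event days, and a Groups 1-4 participant who completed the study, so that the imputed end is Day 237.

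**Rule 3 example.** An unsolicited AE starts on Day 60 and its stop date is blank. An SAE with the same preferred term runs from Day 200 to Day 205.

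1. Step 1 sets the first end date to Day 237.
2. Overlap exists because 200 ≤ 237. This is automatic for any later record, since none in the analysis can start after the imputed end.
3. Remark 2 counts Day 237 as complete, so Remark 1 no longer blocks combination.
4. The records start in post-dose 2 (active) and in its follow-up (non-active), so rule 3 makes them one AE.

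| Stop date of the Day 60 AE | Result | SAE period | SAE onset | Duration |
|---|---|---|---|---|
| Blank, Remark 2 applied | One AE | Post-dose 2 | Day 60 | 237 − 60 + 1 = 178 days |
| Blank, Remark 1 only | Two AEs | Post-dose 2 follow-up | Day 200 | 205 − 200 + 1 = 6 days |
| Month and year only | Two AEs (not imputed, so Remark 1 blocks) | Post-dose 2 follow-up | Day 200 | 6 days |
| Recorded as Day 65 | Two AEs (no overlap) | Post-dose 2 follow-up | Day 200 | 6 days |

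The SAE onset moves by 200 − 60 = 140 days. The first and third rows also show that less information produces more merging.

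**Rule 2 example.** Two same-term records start in post-dose 2: one on Day 58 with a blank stop date, the other on Days 80-82. With Remark 2 they become one AE lasting 237 − 58 + 1 = 180 days. Under Remark 1 alone the second lasts 82 − 80 + 1 = 3 days and the first has no duration. The end point is administrative, not resolution as in SAP 5.1.2. That section lists duration tables for solicited events only, so the effect reaches a table only if solicited records are combined. Otherwise it sits in the analysis dataset and listings.

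**Size of one moved SAE on a period-specific rate** (planned group sizes):

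- Groups 1 to 3: 1/234 = 0.43 percentage points
- Group 5: 1/50 = 2 points
- Group 4 (placebo): 1/39 = 2.56 points

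The count of participants with an SAE over the whole study is the same with or without the merge.

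**The case against.** The strongest reply is that a blank end date conventionally means ongoing. SAP 4.5 says so for concomitant therapies. On that reading a partial date shows that the event ended and a blank one that it did not, which explains the different treatment. For truly ongoing events this stands. But Attachment 2 does not state that premise for AEs and does not tie Remark 2 to a recorded outcome, so a resolved event with a blank stop date is handled in the same way.

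The effect is also contained. Entries are queried and reviewed (Protocol 17.5 and 17.6), the individual records are retained, SAEs get listings or narratives, and SAP 5 plans no formal group comparisons. A shift towards the vaccination window does not hide harm. All of this stands and limits the importance of the point.

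A reader might infer four stronger conclusions that the documents do not support.

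- *A post-dose 1 AE absorbs an SAE that occurs after Dose 2.* Rule 3 does not say whether the non-active period must directly follow the active one, and the natural reading is that it must. The example above needs only adjacent periods. Nor does Attachment 2 say that a solicited reaction merges with an unsolicited SAE, so the example uses an unsolicited event.
- *The same records group differently at successive database locks because the cut-off moves.* With the same recorded dates, a pair present at two locks overlaps at both. Only the combined duration can change.
- *Mean durations are inflated across all events with blank stop dates.* Total duration is assigned only when records are combined, so a single uncombined record is unaffected by Remark 2.
- *SAP 5.1.4 forbids the imputation.* It is a general statement, and Attachment 2 is the specific rule for AE end dates. The two sit awkwardly together, but 5.1.4 does not settle how Remark 2 operates.

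**Conclusion.** The point holds in a limited form. As written, Remark 2 allows an AE that resolved on an unrecorded date to absorb a later same-term record in the follow-up of the same dose. The later record, mostly an SAE, then carries the wrong period and onset. Under rule 2 a combined duration can also run to an administrative date.

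The effect needs several things in one participant: an AE in a post-dose period, resolution without a stop date still unrecorded at lock, and a later record of the same preferred term. It should be rare. The documents give no rate of missing AE end dates, so its frequency cannot be estimated. Per case it adds 0.43, 2 or 2.56 percentage points to a period-specific SAE rate for groups of 234, 50 or 39. The analyses affected are descriptive. Whole-study SAE counts, the immunogenicity endpoints and the hypothesis tests are untouched. Severity is minor and the change is optional.

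**What to change.** Reword Remark 2 along these lines:

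> An imputed end date is considered complete for combining events only when the AE is recorded as ongoing or not resolved. Otherwise Remark 1 applies, the records stay separate, and each keeps the period of its own start date.

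The cost is one sentence in the SAP and one programming condition on AE outcome. SAP 5.1.2 tabulates AEs with fatal outcome, so an outcome field appears to be available. That is an inference, because the documents do not show the eCRF. Truly ongoing events are handled as now.

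Durations based on an imputed end date should not also be dropped from the summaries. For ongoing events that would remove the longest durations and bias the summaries downward.
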